7.2.1. Eye Drop Options

During this study, different eye drops will be tested to mitigate ocular events. Investigators and participants will be informed of which eye drop regimen(s) they should use before the start of study treatment. Participants are required to receive prophylactic lubricating artificial tears and may receive additional eye drop(s) as prophylaxis as recommended by the investigators and Sponsor.

A formal voluntary ocular sub-study may be used to assign participants to different eye drop regimens to compare the frequency and severity of ocular AEs (Section 4.1.3).

Lubricating Artificial Tears

All participants should be instructed to use lubricating artificial tears for the treatment and prophylaxis of ocular symptoms and signs, as directed by the product label or the treating physician. Participants should start their regimen of lubricating artificial tears prior to each dose of IMGC936 and after dosing continue application at least 4 times per day. Lubricating artificial tears are to be continued indefinitely throughout study treatment, at the ophthalmologist or treating physician's discretion.

Vasoconstricting Eye Drops

If instructed to do so, participants should also use refrigerated, topical vasoconstricting eye drops (ie, prescription strength brimonidine 0.1-0.2% twice daily, or potent adrenergic receptor agonist) unless the risks outweigh the benefits as determined by the treating physician or ophthalmologist (see product label warnings and drug interactions). Vasoconstricting eye drops should be applied within 1 hour prior to dosing of IMGC936 and continued for at least 3 days or throughout study treatment at a frequency as directed by the product label, and at the local ophthalmologist or treating physician discretion. If ocular symptoms occur that may be caused by vasoconstricting eye drops (eg, conjunctivitis, redness, itching, burning, visual disturbance), they may be interrupted or discontinued at the discretion of the local ophthalmologist or treating physician.

Corticosteroid Eye Drops

If instructed to do so, participants should also use prophylactic corticosteroid eye drops and should be instructed to self-administer 1% prednisolone (Pred Forte or equivalent). For Schedule A participants, steroid should be self-administered 6 times daily on the day of dosing through Day 4, and 4 times daily on Day 5 to Day 8 of each cycle during the study. For Schedule B participants, steroid should be self-administered 6 times daily on the day of dosing through 4 days after each dose.

Participants receiving multiple drops should be advised to administer the drops at different times if feasible. Participants are suggested to wait at least 15 to 30 minutes between the administration of different eye drops.

In addition, local ophthalmologists or treating physicians may choose to begin therapeutic corticosteroid eye drops when ocular symptoms or signs occur. These may be used in addition to the prophylactic regimen used.

Cyclosporine Eye Drops

If instructed to do so, participants should also use refrigerated, topical cyclosporine (0.025% - 0.2%) eye drops unless the risks outweigh the benefits as determined by the treating physician or ophthalmologist. Cyclosporine eye drops should be applied within 1 hour prior to dosing of IMGC936 and continued for at least 3 days or throughout study treatment at a frequency as directed by the product label, and at the local ophthalmologist or treating physician discretion unless contraindicated. If ocular symptoms occur that may be caused by cyclosporine eye drops (eg, itching, burning, swelling), they may be interrupted or discontinued at the discretion of the local ophthalmologist or treating physician.

7.2.2. Management of Ocular Symptoms and Signs

Table 7: Management of Ocular Symptoms and Signs

Grade (CTCAE v5.0)	Management	Guidelines for Dose Modification ^a
Grade 1	Complete eye examination. Participants should have weekly symptomatic ocular assessments to monitor for worsening symptoms and signs and repeat eye examinations as needed.	Continue study drug dosing.
Grade 2	Complete eye examination. Participants should have weekly symptomatic ocular assessments and repeat eye examinations at least every 6 weeks until resolved to Grade 1 or less, stabilized, or returned to baseline, even after treatment discontinuation, if needed.	Hold study drug dosing until AE has resolved to ≤ Grade 1. Participants whose ocular symptoms and signs resolve to ≤ Grade 1 in ≤ 14 days may be allowed to resume study drug at the same dose level. Participants whose ocular symptoms and signs resolve to ≤ Grade 1 in > 14 and ≤ 28 days may resume study drug at 1 lower dose level with sponsor approval.
Grade 3	Complete eye examination. Participants should have weekly symptomatic ocular assessments and repeat eye examinations at least every 6 weeks until resolved to Grade 1 or less, stabilized, or returned to baseline, even after treatment discontinuation, if needed.	Hold study drug dosing. Participants whose ocular symptoms and signs resolve to ≤ Grade 1 in ≤ 28 days may resume study drug at 1 lower dose level with sponsor approval.

Grade (CTCAE v5.0)	Management	Guidelines for Dose Modification ^a
Grade 4	Complete eye examination. Participants should have weekly symptomatic ocular assessments and repeat eye examinations at least every 6 weeks until resolved to Grade 1 or less, stabilized, or returned to baseline, even after treatment discontinuation, if needed.	Permanently discontinue study drug.

Abbreviations: AE: adverse event; CTCAE: Common Terminology Criteria for Adverse Events.

Note: All participants are recommended to have an EOTV ophthalmic examination, regardless of whether they reported any ocular symptoms or signs. Participants with ongoing Grade 2 or greater ocular symptoms or signs must continue to have ophthalmic examinations at EOTV and during the follow-up period.

7.3. Diarrhea

Participants should be monitored closely for evidence of diarrhea or other change in bowel habits. Participants with diarrhea should be treated accordingly per institutional standard practice. Guidelines for dose modification are provided in Table 8.

Table 8: Dose Modification for Diarrhea

Grade (CTCAE v5.0)	Guidelines for Dose Modificationa
Grade 1	Closely monitor until resolution. No dose reduction required.
Grade 2	Hold study drug until resolved to baseline or ≤ Grade 1. No dose reduction required
Grade 3 (despite use of optimal anti-diarrheal treatment)	Hold study drug until resolved to ≤ Grade 1, then resume at 1 lower dose level
Grade 4	Permanently discontinue study drug

Abbreviations: CTCAE: Common Terminology Criteria for Adverse Events.

7.5. Pneumonitis

The risk of noninfectious pneumonitis due to IMGC936 is unknown. Noninfectious pneumonitis may result in fatigue, shortness of breath, cough, or respiratory distress. Drug induced pneumonitis may be immediately life threatening. If a participant presents with signs or symptoms consistent with pneumonitis and/or other clinically meaningful signs or symptoms of pulmonary toxicity, the participant should be evaluated immediately (evaluation for infection including COVID-19 should be performed). Participants are advised to notify their treating physician immediately if they experience new or worsening shortness of breath, cough, or respiratory distress. Participants who are asymptomatic may continue dosing of IMGC936 with close monitoring.

The management and treatment guidelines outlined in Table 9 should be followed.

Table 9: Management of Noninfectious Pneumonitis

Grade (CTCAE v5.0)	Definition (CTCAE v5.0)	Medical Management of Pneumonitis	Guidelines for Dose Modification ^a
Grade 1	Asymptomatic; clinical or diagnostic observations only; intervention not indicated.	Radiologic assessments (CT scan and/or chest x-ray) should be performed as clinically indicated. Monitor for pulmonary symptoms.	Continue dosing in asymptomatic participants and monitor closely.
Grade 2	Symptomatic; medical intervention indicated; limiting instrumental ADL	Radiologic assessments (CT scan and/or chest x-ray) should be performed as clinically indicated. Participant must be evaluated by a pulmonary specialist. Treatment with corticosteroids may be indicated as recommended by a pulmonary specialist and/or institutional guidelines.	Hold dosing until symptoms resolve to ≤ Grade 1. Study drug may be resumed at same dose level or 1 dose level lower after discussion with the sponsor.
Grade 3	Severe symptoms; limiting self-care ADL; oxygen indicated	Radiologic assessments (CT scan and/or chest x-ray) should be performed as clinically indicated. Participant must be evaluated by a pulmonary specialist. Treatment with corticosteroids until resolution of symptoms may be indicated as recommended by a pulmonary specialist and/or institutional guidelines. Bronchoscopy with lavage and/or biopsy when clinically feasible should be performed. The pneumonitis event must be followed until resolution.	Permanently discontinue study drug.
Grade 4	Life-threatening respiratory compromise: urgent intervention indicated (eg, tracheotomy or intubation)	Manage as Grade 3 event. Hospitalize and initiate maximal supportive care. Urgent intervention may be indicated.	Permanently discontinue study drug.

Abbreviations: ADL: activities of daily living; CT: computed tomography; CTCAE: Common Terminology Criteria for Adverse Events.

^a Failure to meet guidelines for dose modification after the missed dose due to insufficient recovery from a treatment-related toxicity will result in treatment discontinuation unless otherwise specified in the specific management guidance for a particular toxicity (see Section 4.5.1 for details).

7.6. Interstitial Cystitis

Participants should be monitored closely for evidence of interstitial cystitis. Investigators should contact the medical monitor for management of interstitial cystitis.

- Grade 1 interstitial cystitis No specific therapy required; close monitoring of renal function and urinalysis. Consider oral H1-antihistamine or tricyclic antidepressant for symptom management. Recommend participant maintain hydration with oral intake of fluids.
- Grade 2 interstitial cystitis Hold study drug.
 - Administer intravenous fluids for hydration
 - Begin corticosteroids: 1 to 2 mg/kg of oral prednisone or equivalent per day divided twice daily. Taper over 4 weeks as clinically indicated.
 - Resume study drug administration at next scheduled dose if:
 - Interstitial cystitis resolves to \leq Grade 1 within 14 days.
- Grade 3 and 4 interstitial cystitis Permanently discontinue study drug.
 - Consider hospitalization, urology consultation, and biopsy to confirm interstitial cystitis.
 - Begin corticosteroids: 2 to 4 mg/kg of oral or IV methylprednisolone or equivalent per day divided twice daily. Taper over 4 weeks as clinically indicated.

7.7. Hematologic Toxicity

No specific treatment or study drug holds are required for lymphopenia, regardless of CTCAE grade.

7.7.1. Neutropenia

- Grade 1 or Grade 2 No specific therapy required.
- Grade 3
 - Hold study drug until recovery to \leq Grade 1.
 - Monitor neutrophil counts weekly until recovery to \leq Grade 1.
 - Discontinue study drug if not recovered to ≤ Grade 1, within 21 days.
 - Restart study drug at the same dose level if recovered to ≤ Grade 1 within 21 days.
 - Consider secondary prophylaxis with granulocyte colony-stimulating factor (G-CSF) for subsequent cycles.
- Grade 4
 - Hold study drug until recovery to \leq Grade 1.

- Monitor neutrophil counts weekly until recovery to \leq Grade 1.
- Discontinue study drug if not recovered to ≤ Grade 1 within 21 days.
- Restart study drug with one level dose reduction if recovered to \leq Grade 1.
- Consider secondary prophylaxis with G-CSF for subsequent cycles.

7.7.2. Thrombocytopenia

- Grade 1 or Grade 2 No specific therapy required.
- Grade 3
 - Hold study drug until recovery to \leq Grade 1.
 - Monitor platelet counts weekly until recovery to \leq Grade 1.
 - Discontinue study drug if not recovered to \leq Grade 1 within 42 days.
- Grade 4
 - Hold study drug until recovery to \leq Grade 1.
 - Monitor platelet counts weekly until recovery to \leq Grade 1.
 - Discontinue study drug if not recovered to ≤ Grade 1 within 21 days.
 - Restart study drug with one level dose reduction if recovered to \leq Grade 1.

8. CONCOMITANT THERAPY AND RESTRICTIONS

8.1. Concomitant Therapy

All concomitant medications, including prophylactic pre-infusion medications (ocular prophylaxis regimens detailed in Section 7.2.1), and blood products administered during the participant's participation in the study until the EOTV must be recorded in the source document and eCRF. All changes in infusions, including interruptions and their duration as well as reductions in rate and duration, must be recorded.

Please consult the treating physician for any questions related to concomitant medications including known drug interactions and side effects.

8.1.1. Prohibited Therapy

CYP3A4/5 is implicated in the metabolism of DM50 and DM51. Therefore, strong CYP3A inhibitors and inducers, if clinically feasible, should be avoided as concomitant medications for at least 14 days prior to start of treatment and throughout the study or used with caution if critical to the participant's ongoing care. See Appendix 7 for a list of strong CYP3A inhibitors and inducers.

The following rules concerning concurrent treatment(s) apply in this study:

- Any other anti-neoplastic therapies including but not limited to, chemotherapy or other small molecules, biologics, or radiotherapy are not allowed.
 - Anticancer vaccines are considered concomitant cancer therapy and are prohibited from use during the study.
 - Palliative radiation may be allowed for participants who have local symptoms but overall clinical benefit with sponsor approval. Participant needs to pause study drug during the radiation and may resume the treatment after radiation related adverse events return to baseline. The restart of treatment requires the approval from sponsor.
- Participants may not receive other investigational drugs during the period of study participation.
- Use of corticosteroids should be limited to the extent possible (except as specified in this protocol).
- Primary prophylactic use of G-CSF, granulocyte-macrophage colony stimulating factor (GM-CSF), or other growth factors is prohibited during the first cycle of study drug. Use of growth factors with successive cycles of study drug may be considered on a case by case basis in consultation with the sponsor.
- Inactivated annual influenza vaccination and COVID-19 vaccination are allowed and the sponsor recommends they be administered no less than 5 days before or after the dose of study drug, when feasible, to avoid overlapping AEs.

IMGC936 ImmunoGen, Inc Clinical Study Protocol: IMGC936-0901 Amendment 3 29 March 2022

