1.1.3 Special Considerations Regarding Lesion Measurability

Bone lesions, cystic lesions, and lesions previously treated with local therapy require comment: Bone lesions:

- Bone scan, positron emission tomography scan or plain films are not considered adequate imaging techniques to measure bone lesions. However, these techniques can be used to confirm the presence or disappearance of bone lesions.
- Lytic bone lesions or mixed lytic-blastic lesions, with identifiable soft tissue components, that can be evaluated by cross sectional imaging techniques such as CT or MRI can be considered as measurable lesions if the soft tissue component meets the definition of measurability described above.

• Blastic bone lesions are non-measurable.

Cystic lesions:

- Lesions that meet the criteria for radiographically defined simple cysts should not be considered as malignant lesions (neither measurable nor non-measurable) since they are, by definition, simple cysts.
- 'Cystic lesions' thought to represent cystic metastases can be considered as measurable lesions, if they meet the definition of measurability described above. However, if non-cystic lesions are present in the same participant, these are preferred for selection as target lesions.

Lesions with prior local treatment:

• Tumor lesions situated in a previously irradiated area, or in an area subjected to other loco-regional therapy, are not considered measurable unless there has been demonstrated progression in the lesion prior to study enrollment.

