## **6.1.** Efficacy Outcomes

The response outcomes such as best overall response and overall response rates will be determined based on the response data recorded on the Response and Response Follow-up eCRFs between the date of the first dose of study drug and the date of study discontinuation.

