#### 6.1.1. Progression-free survival (PFS)

Progression-free survival will be defined as the time from the first dose date of study drug to the date of first documented progression or death from any cause, whichever occurs first. The documented progression is determined by objective assessment of disease per RECIST v1.1. For participants who are not known to be dead or progressed at the time of data cut-off for PFS

analysis, the PFS will be censored at the date of the last tumor assessment. Specifically, the following censoring rules (Table 2) will be applied to the PFS analysis.

**Table 2:** Censoring rules for PFS

Situation	Date	Outcome	
No baseline tumor assessments	First dose date	Censored	
Death prior to first scheduled tumor assessment	Date of death	Event	
No post-baseline tumor assessments in absence of death prior to first scheduled tumor assessment	First dose date	Censored	
Documented progression	Date of progression	Event	
Initiation of alternative anti-cancer treatments in absence of documented progression	Date of last tumor assessment on or prior to initiation of such treatment	Censored	
Death or documented progression immediately after missing 2 or more consecutive scheduled tumor assessments (i.e, documented progression or death date - last radiological assessment date +1 ≥ 105 days)	Date of last tumor assessment prior to missed assessments	Censored	

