## 7.2. Adverse Events (AEs)

AEs will be documented on the AE eCRF and monitored continuously throughout the study from the time of informed consent until 30 days after the patient's last study drug or until the event has resolved, stabilized, or returned to baseline. AEs attributed to study procedures, including those events that occur prior to the first dose, should also be documented on the AE eCRF.

AE data are available to ImmunoGen from 2 sources, the eCRFs and the serious adverse event (SAE) forms. While reconciliation will be performed, the production of data summaries and listings will be based on the data collected on the eCRF.

Pre-treatment AEs are defined as AEs with an onset date prior to the first dose of study drug. TEAEs are defined as AEs with an onset date on or after the first dose of study drug, and within 30 days of the last dose of study drug or prior to the start of a new anti-cancer treatment, whichever occurs first. Medical history conditions that exist before the initiation of study drug but worsen in severity during the study will also be recorded on the AE eCRF as an AE and will be included as treatment-emergent in the summary tables and listings.

The adverse events will be coded using MedDRA, associating lower-level terms with PT and SOC by the primary hierarchy. The tables will display the counts and percentages of patients who reported at least 1 TEAE in each SOC represented in the AE data. Within each SOC, the tables will display the counts and percentages of patients reporting at least 1 TEAE as designated by the PT.

AEs are graded using Common Terminology Criteria for Adverse Events (CTCAE) Version 5.0. AE summaries may include summaries for all AEs and by the maximum CTCAE grade for the item being summarized (ie, SOC or PT). In these cases, the outputs will include a row for All Grades as well as rows for the 5 potential CTCAE grades, Grade 1 (Mild), Grade 2 (Moderate), Grade 3 (Severe), Grade 4 (Life threatening or disabling), or Grade 5 (Death). AEs missing a severity grade will not be included in the Grade 1-5 rows of the tables. An AE reported by a patient more than once will be represented in the most severe category.

Ocular AEs including blurred vision events and grouped keratopathy events will be analyzed for outcome, resolution, time to onset and time to resolution. Patients at 6mg/kg who administered different prophylactic eye drops will be further analyzed.

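### No rule covers a target lesion irradiated on study, so shrinkage from permitted palliative radiation can count toward a partial response in the primary expansion ORR

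*Protocol*

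**What the plan says.** **The permission.** Protocol 8.1.1 opens with a general bar: "Any other anti-neoplastic therapies including but not limited to, chemotherapy or other small molecules, biologics, or radiotherapy are not allowed". A sub-bullet then relaxes it: "Palliative radiation may be allowed for participants who have local symptoms but overall clinical benefit with sponsor approval". Study drug is paused during radiation, and the participant "may resume the treatment after radiation related adverse events return to baseline", with a further sponsor approval to restart. The text neither restricts nor names the lesions that may be irradiated.

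**Irradiated lesions.** Protocol Appendix 6, section 1.1.3, says that lesions in an area already irradiated "are not considered measurable unless there has been demonstrated progression in the lesion prior to study enrollment". The note under exclusion criterion 3 in Section 5.2 makes the same kind of statement. Both concern the baseline choice of measurable disease.

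**Response.** PR in Appendix 6, section 2.3.1, is a fall of 30% or more in the sum of target diameters from baseline, with no condition on its cause. SAP 6.1 says that response outcomes "will be determined based on the response data recorded on the Response and Response Follow-up eCRFs", from first dose to study discontinuation. Appendix 6, section 2.4, takes best overall response up to the end of treatment. CR and PR need confirmation at least 4 weeks later (Protocol 14.7.1, SAP 6.1.2).

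**Cut-offs.** One censoring row for PFS, also used for DoR, reads "Initiation of alternative anti-cancer treatments in absence of documented progression". The TEAE window in SAP 7.2 runs to 30 days after the last dose "or prior to the start of a new anti-cancer treatment, whichever occurs first". Neither rule says whether permitted palliative radiation counts.

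**The concern.** A participant with a painful target lesion can have it irradiated, resume IMGC936, and be scanned on schedule with that lesion still in the sum of diameters. If the lesion shrinks because of the radiation, the recorded overall response can reach PR, and the SAP takes it as recorded. That response is credited to IMGC936.

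ORR is the primary endpoint of the expansion phase. Each cohort is gated at 2 responders of 13 and is judged in Protocol 14.1 at 7 of 39. With counts this small, one wrongly credited responder changes the estimate and can change whether a cohort continues. A smaller matter is that the documents do not say how permitted palliative radiation is classed for PFS and DoR censoring and for the safety window, so two programmers could build different tables.

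**Working it through.** **1. Which rules reach a lesion irradiated on study?**

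| Rule | Place | Reaches on-study radiation? |
|---|---|---|
| Measurability of irradiated lesions | Appendix 6, 1.1.3 | No, baseline only |
| Note on irradiated lesions | Protocol 5.2, criterion 3 | No, baseline only |
| PR definition | Appendix 6, 2.3.1 | Applies to the whole sum, whatever the cause |
| BOR data window | SAP 6.1; Appendix 6, 2.4 | No stop at radiation |
| 4-week confirmation | Protocol 14.7.1; SAP 6.1.2 | Tests persistence, not cause |

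**2. When can radiation alone give a PR?** Let w be the irradiated lesion's share of the baseline sum and s its proportional shrinkage, with the other target lesions unchanged. PR is met when w × s ≥ 0.30, that is, s ≥ 0.30/w.

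- w = 1 (a single target lesion): s ≥ 30%
- w = 0.6 (60 mm of 100 mm): s ≥ 50%; 60 + 40 = 100 mm becomes 30 + 40 = 70 mm, a fall of exactly 30%
- w = 0.3: the lesion must disappear
- w = 0.2 (one of five equal lesions): not possible from radiation alone, since the largest fall is 20%

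The lesion sizes are invented. The risk lies with participants whose sum is dominated by one lesion.

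**3. The protocol's own design (Protocol 14.1).** Inputs are p0 = 9% (I read the garbled null as 9% or less), p1 = 25%, one-sided 0.05, 80% power, continue at ≥ 2 of 13, reject at ≥ 7 of 39. The exact formula is

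P(reject) = Σ(x = 2 to 13) P[Bin(13, p) = x] × P[Bin(26, p) ≥ 7 − x].

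- At p = 0.09: 0.0454. At p = 0.25: 0.809.
- Chance of meeting the gate at 9%: 1 − 0.91^13 − 13 × 0.09 × 0.91^12 = 1 − 0.2934 − 0.3773 = 0.329.

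The stated 80% power and N = 39 reproduce.

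**4. One false responder, given that it has occurred, at a true ORR of 9%.**

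- In the first 13, the gate then needs at least 1 of the other 12: 1 − 0.91^12 = 1 − 0.3225 = 0.678, against 0.329.
- Effect on the estimate: 1/13 = 7.7 percentage points at stage 1, and 1/39 = 2.6 points at the end. For example, 6/39 = 15.4% (exact 95% CI 5.9% to 30.5%) becomes 7/39 = 17.9% (7.5% to 33.5%).
- Under the Protocol 14.1 test only, the chance of rejecting the null goes from 0.045 to 0.114 if the false responder is in stage 1, or 0.090 if in stage 2.

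**5. As a rate.** The documents give no frequency of on-study radiation, so I assume a share q of true non-responders counted as responders. The apparent ORR is 0.09 + 0.91q.

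| q (assumed) | Apparent ORR | Gate met |
|---|---|---|
| 0 | 9.0% | 0.329 |
| 1.25% | 10.1% | 0.385 |
| 2.5% | 11.3% | 0.440 |
| 5% | 13.6% | 0.542 |
| 10% | 18.1% | 0.711 |

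**6. A remedy that is too broad also costs.** If irradiated participants were simply made non-responders and this removed 5%, 10% or 20% of true responders (assumed), power at a true 25% would fall from 0.809 to 0.767, 0.718 or 0.598. The rule should therefore act on the lesion and on timing.

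**The case against.** The strongest reply is that such a response would be rare. Radiation requires local symptoms, overall clinical benefit and sponsor approval, with a second approval to restart. Up to five target lesions are summed, and the response must be confirmed. All of this lowers the probability, but none of it closes the gap. No approval condition mentions target lesions, and shrinkage that persists for 4 weeks confirms whatever its cause. Nor does the text expressly allow radiation at every site; that is read from its silence.

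It is also fair to say that the 0.33-to-0.68 figure assumes the false responder already exists, and that meeting the gate permits further enrollment without requiring it.

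A reader might infer an inflated type I error. Protocol 14.1 supports that arithmetic, but SAP 4.9 and 4.10 say that no hypothesis test will be done, and the SAP governs the analysis. The effect to rely on is therefore that on the gate, the ORR and its interval.

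A reader might also infer that radiation closes the safety window while IMGC936 is still being given, so that on-drug toxicity is lost. The documents point the other way. The protocol's Synopsis, Section 12 and Section 12.2.1 tie the end of AE assessment to therapy that follows study drug. SAP 4.3 lists the start of later anti-cancer therapy apart from concomitant procedure dates, SAP 4.3.3 handles prior radiotherapy as a procedure, and SAP 7.7 keeps concomitant procedures distinct from new anti-cancer treatment. On-study palliative radiation is most naturally a concomitant procedure. What stands is that no sentence says so, while 8.1.1 groups radiotherapy with anti-neoplastic therapy.

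**Conclusion.** The concern holds for response. Following the plan as written, shrinkage of a target lesion irradiated on study can count toward PR in the primary expansion ORR and toward the 2-of-13 gate, and no rule in either document prevents it. The size is conditional. One false responder among the first 13 at a true 9% ORR moves the chance of meeting the gate from 0.33 to 0.68, and one among 39 moves the final ORR by 2.6 points. The expected effect cannot be given, because the documents contain no frequency for on-study radiation.

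For the safety window and for PFS and DoR, only a clarification is needed. It would be too strong to say that classing radiation either as new anti-cancer treatment or as a procedure must give a wrong result: each can be defended for a given endpoint once it is stated. Nor do on-drug scans stop at radiation, since the rule ending tumor assessments at another anticancer therapy is written for participants who have already stopped study drug. The point should be settled before the response data are reviewed, because in an open-label study a later choice would be made knowing who responded.

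**What to change.** **Response (SAP 6.1.2 and Protocol 14.7.1).** State that from the date of radiation an irradiated target lesion cannot contribute shrinkage to response:

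- For CR and PR it is carried at its last pre-radiation diameter. Progression still counts.
- A CR or PR first seen after radiation does not count unless the non-irradiated target lesions alone bring the sum to the threshold. In the 60 and 40 mm example the sum stays at 60 + 40 = 100 mm and there is no PR. The 40 mm lesion would have to fall to 10 mm for the sum to reach 70 mm.
- Responses confirmed before radiation stand. A PR first seen before radiation may still be confirmed on the same basis, so genuine responses are not discarded.

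**Clarifications.** In SAP 7 and 7.2, state that permitted palliative radiation during continuing IMGC936 is a concomitant procedure and does not close the safety or TEAE window. In SAP Table 2 and Protocol Table 11, state whether it counts as alternative anti-cancer treatment for PFS and DoR.

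**Cost.** A few sentences, a target-lesion flag on the radiation record, and an occasional real response not credited, chiefly where the irradiated lesion makes up most of the sum. These are analysis rules only; the clinical permission in 8.1.1 is unchanged.
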